### **Background on MDR notification rates at partner institutes**

The partners in the proposal expect to recruit at least 80% of the eligible retreatment patients (those with rifampicin resistance and the next rifampicin sensitive patient) presenting for diagnosis and care. The expected numbers of rifampicin-resistant TB are as follows:

**Table 2.** Annual new Rifampicin-resistant (RR) TB diagnoses among patients at the African partner institutions

Estimated RR-TB patients diagnosed /year	
Benin, LRM	30
Cameroon, TBRL (*)	80
DRC, INRB	150
Ethiopia, JU	55
Guinea, GNRL	100
Mali, SEREFO	20
Nigeria, DF	55
Rwanda, RBC	90
Senegal, CHUD	10
Total	590

### **Background on MDR treatment monitoring**

Currently, culture on monthly sputum samples is recommended by WHO for follow-up of MDR-TB patients under treatment (11), who are monitored through the end of their treatment. Unfortunately, culture is often not locally available and samples need to be transported from field to culture laboratories. The associated transport delays lead to high rates of contamination and false negative culture, thus leading to missing and unreliable data, particularly in laboratories in low resource settings. Even when locally available, negative cultures require 42 days of incubation, with the associated delay in knowing whether a patient is responding to therapy (5).

### **Technical background – FDA**

Fluorescein DiAcetate (FDA) microscopy is a low cost diagnostic based on the FDA ester that needs to be cleaved by enzymes in live bacteria before it fluoresces, and slides can be read in the same fluorescent microscopes used for auramine microscopy (6). Preliminary results suggest that FDA vital stain microscopy correlates strongly with culture in MDR patients on follow-up.

### **Technical background – Xpert MTB/Rif**

Similarly, we hypothesize that the now widely available Xpert MTB/Rif assay can be used to follow the decline in bacterial load, akin to the measurement of viral loads for the monitoring of HIV patients on therapy (12). We expect that the slope of the decline will be predictive of successful outcome.

### **Technical background on the connectivity solutions for GeneXpert**

The Xpert has revolutionized the rapid diagnosis of RIF resistance in endemic settings, yet the logistics of data reporting can be challenging.

The GeneXchange™ system, now improved as DataToCare is an information technology solution for capturing and analyzing data linked to Xpert, developed for low resource countries. This software permits to capture data directly from the laptop of the Xpert machine, such as the test results, including precise information such as cycle threshold (Ct) and individual probe results, basic epidemiological information and basic clinical data. This information is then sent by SMS or internet to a central server, which allows consultation, analysis and exportation of data using a web interface. The connectivity solutions will target the Xpert results and Specific systems will be developed to allow data capture and transmission of the novel tests.

## **2. Rationale**

We anticipate that the impact of the DIAMA project, if the results are as promising as expected, will be potentially paradigm-shifting. We foresee that MDR-TB will move from an often terminal illness with grave prognosis to a readily recognizable and treatable disease, in which treatment success can be predicted early, so treatment can be modified in 'real' time. The novel tests that identify specific resistance to particular drugs used for the treatment of resistant TB allow for a way of 'personalized medicine', and by monitoring the impact of specific mutations on the outcome of MDR treatment, we anticipate learning which mutations should lead to treatment modifications in order to enhance the chance of treatment success. In addition, we will learn whether heteroresistance, which is the simultaneous occurrence of bacterial populations with and without resistance, is of clinical relevance. Lastly, the fact that the Deeplex assay gives full sequence information on a large number of genes allows us to detect, for the first time, whether different mutations are common in circulating drug resistant strains in the participating countries in Sub-Saharan Africa. Such results will thus not only inform the treatment algorithms used in clinical trials for MDR-TB, yet also provide fundamental insights into the pathogenesis underlying the development of TB resistance.

Once the validation of the novel diagnostic tests for TB resistance mutations will be completed in the DIAMA proposal, the companies that have developed these tests will

include these results in their respective applications for approval by regulatory authorities, and for endorsement by WHO. The monitoring of MDR patients on treatment with FDA microscopy is readily implementable in most peripheral microscopy centers.

## Study Objectives

### 1. Overall Aim:

To improve diagnosis and management of MDR-TB patients with culture-free approaches

### 2. Primary objectives:

1. To diagnose TB resistance to 1st and 2nd line drugs through novel molecular multiplex assays (Study 1)
  - a. To validate the Deeplex assay and establish a network for shipment of sputum samples in ethanol to regional reference laboratories (Study 1 – phase 1)
  - b. To validate the InSilixa chip-based detection of resistance as a point of care test (Study 1 – phase 2)
  - c. To validate the Cepheid Xpert 2nd line cartridge at the district level
2. To setup alternative culture-free approaches for the monitoring of patients' response to MDR treatment (Study 2), with:
  - a. FDA microscopy
  - b. Measurement of bacterial load by following Cycle threshold (Ct) values in Xpert MTB/Rif

### 3. Secondary objectives:

1. To estimate the proportion of additional resistance in patients resistant to RIF (isoniazid, and other drugs) in the countries involved using the novel validated tests and identify associations of programmatic outcome in MDR patients.
2. To measure the association of specific mutations against INH and PZA with programmatic treatment outcome
3. To pilot whether implementation of DataToCare for real-time monitoring of molecular test results can reduce delay between diagnosis and treatment of RR-TB patients

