## 5. Study outcomes

- For the study 1 (validation of deeplex test, Insilixa and Xpert 2nd line):

Drug resistance to INH, RIF, ofloxacin, kanamycin as measured by phenotypic methods and Deeplex method.

Secondary outcome: for both RR- and RS patients programmatic treatment outcome will be recorded.

- For the study 2 (cohort study, on RR patients only):

Three types of unfavorable treatment outcomes will be considered:

- Early treatment failure defined as a culture positive at month 6 of the TB treatment (+/- 2 weeks) not followed by negative consecutive cultures and with molecular confirmation of the similarity of the strain with the baseline one
- End of treatment failure defined as a positive culture at the end of the TB treatment (+/- 2 weeks) not followed by negative consecutive cultures and with molecular confirmation of the similarity of the strain with the baseline one
- Relapse defined as a positive culture after the end of the TB treatment not followed by negative consecutive cultures and with molecular confirmation of the similarity of the relapse strain with the baseline one.

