## 6. Data management & Data Collection

### **Data collected:**

For each patient enrolled in study 1 & 2, an expanded laboratory request form will be completed.

For all patients the following data will be collected:

- Baseline characteristics (mostly those collected from routine monitoring, including demographic- and contact information, detailed treatment history including details such as failure vs relapse prior MDR treatment, return after loss to follow-up), risk factors for (resistant) TB
- Phenotypic drug sensitivity tests (phase I of Study 1 only)
- Deeplex results (phase I and II of the Study 1)
- Programmatic treatment outcomes

In addition:

- for the phase 2 of the study 1 (validation of InSilixa and 2nd line Xpert test) the results of these 2 tests (InSilixa and 2nd line Xpert) will also be recorded
- for all patients enrolled as RR, the following additional information will be recorded:
  - monthly FDA results,
  - monthly GeneXpert and culture results,
  - treatment outcomes

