## 8. **Laboratory procedures**

### **Sampling schedule**

The DIAMA project is based on routine diagnosis and patient management.

While country TB programs recommend collecting sputum samples, a maximum of two additional samples will be asked at the same visit.

All patient interventions and associate laboratory tests are summarized in Table 4 below.

**Table 4.** Schedule of assessment

	Screening 	Enrollment 	Follow up 
Medical/demographic history	X		
Informed Consent		X	
Sputum collection	X	X	X
Programmatic outcome follow-up 			X

 Includes routine programmatic interventions

 May be combined with screening

 RR patients only

As no additional visit is required, and intervention is minimal, no compensation fee will be given to the participants.

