### **Specific tests**

In all settings, smear microscopy with Ziehl-Neelsen (ZN) or auramine/rhodamine (A/R), culture, 1st line drug susceptibility testing (DST) and Xpert MTB/Rif are routinely used. Where 2nd line DST on solid culture is not yet available, the project will help implementing the recommended tests on a routine basis. If implementation is not possible in a reasonable framework, respective samples will be tested in one of the study reference labs (LRM Cotonou, RBC Kigali or ITM Antwerp), together with the Deeplex.

Samples will undergo direct auramine microscopy and direct FDA microscopy. All samples (including AFB negative) will undergo Xpert MTB/Rif testing and culture.

As all partners already conduct phenotypic DST, the culture and first-line phenotypic DST will be conducted on-site, following training for second line DST by the Lowenstein Jensen proportion method as necessary. Participating laboratories will receive periodic External Quality Assessment (EQA) panels from the ITM in Antwerp. Surplus sputum will be stored at

-20C and serves for testing additional bacterial diagnostic tests, such as the InSilixa and Cepheid 2nd line tests available in the second phase of study 1.

Partners are moreover encouraged to follow WHO guidelines regarding the use of Line Probe Assays (LPA) for FQ and injectable resistance for RR patients, which is not part of the DIAMA study protocol. Given the intrinsic delays of shipments in phase I, and the fact that the Deeplex is not yet validated in phase I, the use of such LPAs will support the appropriate choice of treatment regimen for RR patients. The partner laboratories will however be able to request results from Deeplex testing to weigh these 'unvalidated' results in the choice of a salvage regimen in case patients fail their RR treatment.

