### **4. Ethical (and Regulatory) Review**

This study will be submitted for formal review and approval to the Benin ethics committee (i.e. the central ethics committee), and the Ethics Committee(s) and/or Competent Authorities of the nine countries where the study is carried out and of selected collaborating partners.

The study will be carried out according to the principles stated in the Declaration of Helsinki, all applicable regulations and according to established international scientific standards.

Each partner will submit the protocol of the studies, including the information sheet and consent form as well as a Material Transfer Agreement on the shipment of samples to the competent body of their country for independent examination of the scientific merits and ethical acceptability. No participants will be enrolled or subject related activities performed in a site, before written approval from the local- as well as the central ethics committees is

obtained. The studies will moreover not start at each site until a copy of a written and dated approval has been received by the project coordinator.

The choice of treatment for the patient will not depend on the results of the test under validation but on locally conducted tests. In case study results are suggestive of discordant results with the local site laboratory, the interpretation of all available results will be discussed with experts in the field to determine whether the patient's standardized MDR regimen would best be adjusted.

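### Table 4 contradicts the plan to record treatment outcome in rifampicin-sensitive patients, and the mutation–outcome objective has no regimen variable behind it

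*Combined protocol and SAP*

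**What the plan says.** **The objective and its purpose.** Item 2 of the Secondary objectives is "To measure the association of specific mutations against INH and PZA with programmatic treatment outcome". It names no population. The Rationale gives the use: relating particular mutations to the outcome of MDR treatment should teach which of them call for a change of treatment.

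**Outcome recording.** Under Study outcomes, for Study 1, "for both RR- and RS patients programmatic treatment outcome will be recorded". Under Data collected, programmatic outcomes are listed below the line "For all patients the following data will be collected". In the Sampling schedule, "All patient interventions and associate laboratory tests are summarized in Table 4 below". The only mark in that table for programmatic outcome is in the Follow up column, whose footnote reads "RR patients only".

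**Regimen data.** Data collected lists baseline characteristics (including treatment before the current episode), phenotypic susceptibility results in phase 1, Deeplex results in both phases, and outcomes. It continues that "for all patients enrolled as RR, the following additional information will be recorded": monthly FDA microscopy, monthly GeneXpert and culture, and treatment outcomes. The current regimen, changes to it and line probe assay (LPA) results do not appear.

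**What steers the regimen.** Under Specific tests, LPAs for fluoroquinolones and injectables are encouraged but lie outside the study protocol, and "the use of such LPAs will support the appropriate choice of treatment regimen for RR patients". The same section lets sites ask for Deeplex results when a salvage regimen is considered. The Ethical (and Regulatory) Review section says "The choice of treatment for the patient will not depend on the results of the test under validation", and then provides for expert discussion of adjusting the standardized regimen when study and local results disagree.

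**Analysis.** The Data Analysis section gives no model, population or covariates for objective 2. Its only outcome model is the Study 2 Cox regression, which concerns the timing of monitoring.

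**The concern.** A site that works from the schedule table would stop outcome collection in rifampicin-sensitive patients, and half of the planned sample would have no value for a stated secondary outcome. Programme outcomes may be hard to recover years later across nine countries.

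The regimen gap bears on interpretation. A result meant to say which mutations should change treatment needs to be read against the treatment given. If carriers of a mutation tended to receive a different regimen, or if sites with different regimens also have different circulating strains, an association (or its absence) could come from the mutation, the regimen, or both. With no regimen field the question cannot be examined at all.

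**Working it through.** **Table 3 counts, reproduced first.** Each phase has 1420 patients, of whom 710 are rifampicin-resistant (RR) and 710 rifampicin-sensitive (RS).

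- Total: 2 × 1420 = 2840, as stated; RS over both phases: 2 × 710 = 1420.
- Isoniazid-resistant among RR: 0.95 × 710 = 674.5, stated as 675.
- Isoniazid-resistant overall: 0.65 × 1420 = 923, as stated.

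**Implied split of isoniazid status, per phase.**

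| | RR | RS | All | Share in RS |
|---|---|---|---|---|
| Isoniazid-resistant | 675 | 923 − 675 = 248 | 923 | 248/923 = 27% |
| Isoniazid-susceptible | 710 − 675 = 35 | 710 − 248 = 462 | 497 | 462/497 = 93% |

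**If Table 4 governs.** Outcome is missing for 1420/2840 = 50% of patients. An isoniazid comparison would be left with RR patients alone, about 2 × 675 = 1350 resistant against 2 × 35 = 70 susceptible over both phases.

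**If Study outcomes and Data collected govern.** No patient is lost by design.

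**Regimen: the sections side by side.**

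| Question | Where | Answer |
|---|---|---|
| Is the result meant to guide treatment? | Rationale | Yes |
| Can resistance results bear on the RR regimen? | Specific tests | Yes, through LPAs, whose use is encouraged but not required |
| Can the standardized regimen be adjusted? | Ethical (and Regulatory) Review | Yes, after expert discussion of discordant results |
| Is the regimen, or a change to it, recorded? | Data collected | Not listed |
| Is there an analysis that accounts for it? | Data Analysis | None given for objective 2 |

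No arithmetic can give the size of the regimen problem. The documents state no outcome rates, regimen frequencies or regimen effects. If regimen is balanced across mutation groups, it does not distort the comparison between them; without regimen data that balance could not be shown.

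**Whether study results can influence treatment.** The Synopsis envisages prompt communication of molecular results so that appropriate treatment starts quickly. The ethics section separates treatment choice from the tests under validation but allows adjustment after discordance. Specific tests allows Deeplex results to be weighed for salvage treatment. These statements need reconciling; which is right is not judged here.

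**The case against.** **On Table 4.** Two sections provide for outcome recording in RS patients, against one footnote. The outcome row also carries a footnote referring to routine programme activity, so outcomes could come from programme records. The flow chart in Annex 1 is not available in the text reviewed. A reader might infer that RS patients are excluded from outcome follow-up; the documents do not support that. They contradict themselves, and the loss is conditional on which text the sites follow.

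**On the isoniazid counts.** Objective 2 names no population, and the Rationale speaks of MDR treatment. If the objective is meant for RR patients only, following Table 4 costs it nothing, though the Study 1 secondary outcome would still be lost in RS patients. This stands, so the 27% and 93% shares are conditional. Pooling RR and RS patients would also mix different treatments.

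**On confounding.** A reader might conclude that the associations are confounded. The documents do not show this. A regimen chosen because of a resistance result is mainly a mediator or effect modifier, and the crude association is then the mutation's total effect under the care actually given. The LPAs in question concern fluoroquinolones and injectables, not isoniazid or pyrazinamide, so they bear on objective 2 only if those resistances differ between mutation groups. Deeplex already genotypes the fluoroquinolone and injectable targets in both phases, so an LPA result is partly redundant.

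**What remains.** Deeplex does not show what was prescribed, when it changed, or what the clinician knew at the time, and nothing else in the data list substitutes for that. Even a total effect can be carried over to other care only if the care behind it is described.

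**On study results and treatment.** The apparent disagreement is narrower than it first looks. The salvage route applies after treatment has failed, the ethics section states its own exception, and the connectivity section is aimed chiefly at Xpert results. Some tension remains.

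**Conclusion.** Both points hold in limited form and should be corrected.

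1. Table 4 contradicts the Study outcomes and Data collected sections. If Table 4 is followed, a stated Study 1 secondary outcome is missing for 1420 of 2840 patients. The isoniazid figures (248 of 923 and 462 of 497 per phase) rest on the Table 3 prevalences and matter to objective 2 only if it includes RS patients.
2. Objective 2 is planned with no regimen or regimen-change variable, no stated population and no analysis, although its purpose is to inform treatment and the documents show that regimens may vary with resistance results. The associations may reflect regimen differences that could be neither examined nor adjusted for. Neither the presence nor the size of such an effect can be derived from the documents.

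The primary validation of the assays against their reference standards is not affected.

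**What to change.** - **Table 4:** split the Follow up column, so that sputum follow-up is for RR patients and programmatic outcome is for all patients, in line with the Study outcomes and Data collected sections.
- **Data collected:** add, from routine treatment records, the drugs in the initial regimen and the start and change dates. Where available, add the LPA result and the date any Deeplex result was released to the site.
- **Data Analysis:** state the population for objective 2 and analyse RR and RS patients separately. Report mutation–outcome associations overall, and stratified by or adjusted for initial regimen and fluoroquinolone/injectable genotype.
- **Later regimen changes:** describe them, but do not exclude those patients. A change can follow failure, so exclusion could selectively remove unfavourable outcomes.
- **Consistency:** reconcile the Synopsis, Specific tests and Ethical (and Regulatory) Review sections on whether study results can influence treatment.

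The cost is one table edit, a few form fields, a short analysis paragraph and modest data entry. No extra visit or sample is needed.

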## Methods

The study is expected to start in the first quarter of 2017, and will end May 31st, 2021.

### 1. Study design:

Two multi center observational studies will be conducted:

- *Study 1:* Cross sectional study for TB cases aged  $\geq 15$  (all RIF resistant (RR) ones (new cases or retreatment patients) and equal number of RIF sensitive retreatment

patients from the same country) with comparison of TB resistance diagnostic test performance at baseline. There are 2 phases in this project; phase 1 is the comparison of Deeplex results against the phenotypic results (Gold standard), phase 2 is the comparison of Insilixa and Xpert 2nd generation results against Deeplex (gold standard).

- *Study 2:* Cohort study of RR-TB patients (recruited in Study 1) under treatment with comparison of the performance of FDA or Xpert compared to solid culture

The study flow chart is placed in annex 1 of this protocol

## **2. Study settings**

The study takes place in nine African countries (Benin, Cameroon, DRC, Ethiopia, Guinea, Mali, Nigeria, Rwanda and Senegal) with patients recruited at a national or regional level (depending on country size), and the samples tested in the respective reference laboratory (see partners). All partners involved in this study have or will implement(ed) a routine system of screening all TB patients at risk for resistant TB aged  $\geq 15$  with Xpert/MTbRif.

## **3. Study population**

In order to be eligible for study 1 and 2, study participants **must meet the following criteria:**

- Being  $\geq 15$  year old
- Having a positive test on GeneXpert (*M. tuberculosis*) with or without resistance detected to rifampicin
- Willing and able to provide written informed consent, or for minors: assent from these patients and consent from a legal representative

In addition, for the study 2 (cohort study), only patients for whom RIF resistance was detected with GeneXpert at baseline and who started MDR-TB treatment will be eligible.

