## **4. Sample size**

The partners in the proposal expect to recruit at least 80% of the eligible retreatment patients (those with RIF resistance -considered as MDR- and equal numbers of RIF sensitive patients) presenting for diagnosis and care. Based on previous years data, over 4700 patients at risk of RR TB are on average collectively being screened annually out of which 590 (15%) are diagnosed as being RR-TB (Table 2, in Background).

For the validation of the novel tests (Study 1), we will recruit all RR patients and equal numbers of RIF susceptible patients, for a total of 1420 RR- and 1420 RIF susceptible patients. In the table below, we summarize the power we expect to have to detect resistance to the key drugs:

**Table 3.** Sample size considerations against **phenotypic** gold standard (Phase 1), and the **genotypic** gold standard (Phase 2, see study flow chart in Annex 1), with each phase including 1420 patients, half of whom will have RR TB, for a total of 2840 patients.

Drug	Expected prevalence of resistance in RIF R (n=710 each phase)	Expected total prevalence of resistance (n=1420 each phase)	Expected sensitivity and precision against phenotypic test	Expected specificity and precision against phenotypic test	Expected sensitivity and precision against genotypic test	Expected specificity and precision against genotypic test
RIF	710 (100%)	710 (50%)	98% +/- 1%	98% +/-1%	98% +/- 1%	98% +/-1%
INH	675 (95%)	923 (65%)	90% +/- 1%	98% +/-1%	98 +/- 1%	98% +/-1%
FQ	43 (6%)	43 (3%)	85% +/- 8%	98% +/-1%	98%, range 88%-100%	98% +/-1%

RIF= rifampicin, INH=isoniazid, FQ=fluoroquinolones

The estimated prevalence of resistance is based on the WHO report (1) and personal communications. This sample size will be ample to validate these tests for resistance to RIF, isoniazid, and fluoroquinolones, according to established guidelines (9).

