## **9. Data Analysis**

For the phase I and II of the study 1 (validation of Deeplex against phenotypic DST & validation of InSilixa and Xpert 2nd generation against Deeplex results), we will validate the molecular assays for their performance (Se and Sp) on the diagnosis of RIF resistance, against phenotypic DST on solid medium as gold standard, with resolution of discordances by classic target sequencing of the *rpoB* gene. Similar analyses will be conducted to determine the performance for the diagnosis of isoniazid and fluoroquinolone resistance.

An interim analysis will be performed after 350 RR-TB patients have been recruited in order to test our assumptions regarding resistance proportions and consider adjustment of sample size or recruitment strategy.

For the study 2, the results will be analyzed with time dependent Cox regression to identify the optimal time point to identify patients who are at risk of failing treatment.

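### Table 3 counts recruited patients, but Phase 1 accuracy can be computed only where both phenotypic DST and Deeplex gave a result; no allowance for loss is stated, and no reporting of patients without a result is planned

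*Combined protocol and SAP*

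**What the plan says.** **Entry.** Methods section 3 admits patients aged 15 or over who consent and meet one laboratory criterion: "Having a positive test on GeneXpert". No culture, DST or Deeplex result is needed.

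**Comparison.** Methods section 1 states: "phase 1 is the comparison of Deeplex results against the phenotypic results (Gold standard". Methods section 9 specifies "against phenotypic DST on solid medium as gold standard". That sentence in section 9 covers both phases, but section 1 makes Deeplex the Phase 2 reference, and section 6 collects phenotypic DST in Phase 1 only.

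**Sample size.** Methods section 4 states: "we will recruit all RR patients and equal numbers of RIF susceptible patients, for a total of 1420 RR- and 1420 RIF susceptible patients". Table 3 is built on this, "with each phase including 1420 patients, half of whom will have RR TB". No rate of culture growth, DST success or Deeplex success is given. The 80% in that section is the share of eligible patients expected to be recruited, not the share expected to yield results.

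**Analysis.** Section 9 plans sensitivity and specificity. Sequencing of *rpoB* resolves discordant results, not missing ones. No analysis population is named, and no rule is given for failed or uninterpretable results. The interim review at 350 RR patients concerns resistance proportions, and may lead to a change in sample size or recruitment.

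**Culture loss.** Section 8 (Specific tests) says: "All samples (including AFB negative) will undergo Xpert MTB/Rif testing and culture". The Introduction, on treatment monitoring, says: "The associated transport delays lead to high rates of contamination and false negative culture".

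**The concern.** Two things are at stake.

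The first is precision. Any patient without a paired result shrinks the denominators from which Table 3's precision is derived. This matters most for fluoroquinolone sensitivity, which rests on 43 resistant cases per phase.

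The second is what the accuracy figures describe, and it matters more. The overall aim is a culture-free approach, with Deeplex applied directly to sputum. If sensitivity and specificity are computed only where a culture grew and Deeplex worked, the result covers a subset of the Xpert-positive patients for whom the test is meant. Those left out are plausibly the patients with few bacilli, for whom a culture-free test would add most. Good sensitivity and specificity could then coexist with a modest rate of usable results, and the planned summaries would not require that rate to be shown. The Rationale expects the results to support regulatory applications and WHO endorsement.

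**Working it through.** **Inputs.** From Table 3: 710 RR and 1420 total patients per phase; the prevalences; Phase 1 sensitivities of 98% (RIF), 90% (INH) and 85% (FQ). Assumed here: two-sided 95% confidence, since no level is stated; an evaluable fraction f of 0.90, 0.80 or 0.70, since none is given; and loss unrelated to resistance.

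**Step 1: reproduce the counts.** Recruited number × prevalence:
- RIF: 710 × 1.00 = 710
- INH: 1420 × 0.65 = 923
- FQ: 1420 × 0.03 = 42.6, rounded to 43

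The counts match exactly with zero loss, so they are counts of recruited patients.

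**Step 2: reproduce the precision.** Half-width = 1.96 × √(p(1−p)/n):
- RIF sensitivity, n = 710: ±1.03 (stated ±1)
- INH specificity 98%, n = 1420 − 923 = 497: ±1.23 (stated ±1)
- INH sensitivity, n = 923: ±1.94 (stated ±1)
- FQ sensitivity, n = 43: 1.96 × √(0.85 × 0.15/43) = ±10.7 (stated ±8)

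The last two do not reproduce at 95% even with no loss. For FQ, ±8 needs 1.96² × 0.85 × 0.15/0.08² = 76.5, so 77 resistant cases. These are separate errors in Table 3, not effects of missing results.

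**Step 3: apply the evaluable fraction** (n × f, same formula, half-widths in points):

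| f | Evaluable per phase | FQ-resistant | FQ Se 85% | INH Se 90% | INH Sp 98% | RIF Se 98% |
|---|---|---|---|---|---|---|
| 1.00 | 1420 | 43 | ±10.7 | ±1.9 | ±1.2 | ±1.03 |
| 0.90 | 1278 | 39 | ±11.2 | ±2.0 | ±1.3 | ±1.09 |
| 0.80 | 1136 | 34 | ±12.0 | ±2.2 | ±1.4 | ±1.15 |
| 0.70 | 994 | 30 | ±12.8 | ±2.3 | ±1.5 | ±1.23 |

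**Step 4: effect of counting failed index results.** If a share d of DST-resistant patients has no Deeplex result and these count as not detected, sensitivity becomes Se × (1 − d). The values of d are assumed:

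| d | RIF (98%) | INH (90%) | FQ (85%) |
|---|---|---|---|
| 5% | 93% | 86% | 81% |
| 10% | 88% | 81% | 77% |
| 20% | 78% | 72% | 68% |

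This choice can move the estimate by more than the half-widths in Step 3, so the handling of failures should be fixed in advance.

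**The case against.** The case on the other side has real force, and much of it stands.

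- *Wrong cause.* A reader might infer that the entry criteria are why the ±8 for fluoroquinolones is not met. They are not. The half-width is ±10.7 with no loss at all, and a 30% loss adds about 2 points. Entry on a positive Xpert is also appropriate for a test on sputum.
- *Wrong phase.* A reader might also apply culture loss to the Phase 2 fluoroquinolone entry, "98%, range 88%-100"%. The Phase 2 reference is Deeplex, so failure to grow does not drive that cell. Only failed Deeplex or index tests would.
- *Support for culture loss.* The Introduction's statement on contamination concerns monthly follow-up cultures in general and gives no baseline rate. Section 8 places culture and first-line DST on site and provides a preservative for shipped sputum. The sentence on AFB-negative samples directly follows one on FDA microscopy and may refer to follow-up. These passages show that loss is foreseeable, not how large it is.
- *Interim review.* Estimating resistance beyond rifampicin requires test results, so a severe shortfall would probably surface. There may also be room to recruit: 590 × 0.80 = 472 RR patients a year, so 1420 takes about 3 years of a study running from early 2017 to May 2021. Neither point sets a yield to check against.
- *Silence is not exclusion.* Section 9 does not say that failures will be dropped or hidden. The Annex 1 flow chart could not be read in the copy reviewed and may contain such a step.

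What remains is that the visible text states no evaluable fraction and no reporting of patients without a result.

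**Conclusion.** The point holds in limited form. It is certain that Table 3's counts assume a complete paired result for every recruited patient, and that any loss reduces the denominators. The size of the loss is not in the documents. Over an assumed 10-30%, only the fluoroquinolone sensitivity is noticeably affected: 43 cases become 39-30, and ±10.7 becomes ±11.2-12.8 points. Rifampicin, and isoniazid specificity, stay near ±1. Isoniazid sensitivity goes from ±1.9 to at most ±2.3.

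The stronger reason to act is interpretive. Without the proportion of enrolled patients who obtain an interpretable result, sensitivity and specificity do not show how the assay serves the Xpert-positive population. The documents do not support any particular usable-result rate, nor the claim that the study cannot reach adequate precision. This is an inexpensive improvement that should be made, not a fault that invalidates the design.

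**What to change.** **Methods section 4.** State an assumed evaluable fraction for each phase: valid DST plus interpretable Deeplex in Phase 1, and interpretable Deeplex plus interpretable index test in Phase 2. Restate Table 3's counts and precision on that basis, naming the confidence level. Recruitment need not increase. The INH and FQ sensitivity entries that fail at 95% without loss should be corrected at the same time, as a separate matter.

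**Methods section 9.**
- Add the observed paired-result yield to the interim review at 350 RR patients.
- Beside each sensitivity and specificity, report the proportion of all enrolled Xpert-positive patients with an interpretable index result, including those whose culture did not grow. Break this down by baseline Xpert Ct where it is captured. Section 6 does not list baseline Ct for rifampicin-susceptible patients, and connectivity is planned for selected sites, so it may be incomplete.
- Add a sensitivity analysis that counts an uninterpretable index result as not detected in reference-resistant patients (DST-resistant in Phase 1, Deeplex-resistant in Phase 2). Other conventions exist; what matters is that one is specified in advance.

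**Cost.** Protocol wording, one extra results table, and slightly less favourable stated precision. No added patients, visits or tests.
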